1. AMENDMENT HISTORY

Amendment No.	CIP Version No.	Date Issued	Author(s) of Changes	Details of Changes

2. LIST OF APPENDICES

Appendix A	Investigator's Brochure
Appendix B	Protocol of the study
Appendix C	Inform Consent Form

3. ABBREVIATIONS

AE	Adverse Event
AR	Adverse Reaction
BCVA	best-corrected visual acuity
CIP	Clinical Investigation Plan
CRA	Clinical Research Associate
CRF	Case Report Form
EC	Ethics Committee (see REC)
GCP	Good Clinical Practise
GP	General Practitioner
IB	Investigator Brochure
ICF	Informed Consent Form
ICH	International Conference of Harmonisation
IRB	Independent Review Board
Log MAR	logarithm of the minimal angle of resolution
PI	Principle Investigator
SAE	Serious Adverse Event
SAR	Serious Adverse Reaction
SUSAR	Suspected Unexpected Serious Adverse Reactions

4. CLINICAL INVESTIGATION SUMMARY

Title	CT Lucia 601 IOL implantation in the sulcus
Reference Number (Acronym)	CLuS
Clinical phase	Post-marketing study (phase 4)
Objectives	To perform a retrospective investigation of the CT Lucia 601 IOL implantation in the sulcus

Endpoints	Primary endpoint: determine whether the CT Lucia 601 IOL can be used safely in the sulcus
Design	Non-commercial (academic with study grant), monocentric, post-interventional observational without use of a study drug
Data Collection	A single late-postoperative visit, scheduled ≥ 6 months after the vitrectomy See Study Flow Chart 7.3
Planned Clinical investigation Period	2019-2020
Clinical investigation population	Patients who had an implantation of the CT Lucia 601 lens
Number of Participants	100
Inclusion/Exclusion Criteria	
Inclusion criteria
 
 • Patients with an implantation of a CT Lucia 601 lens for different reasons: 
 ○ During vitrectomy to treat a complicated cataract surgery and had the implantation of a CT Lucia 601 IOL in the sulcus or patients ○ During phaco surgery with a posterior capsule tear that necessitated the implantation of the implant lens in the sulcus ○ Explantation of an in-the-bag lens and implantation of a CT Lucia 601 as replacement lens (e.g. to treat opacification of the implant lens or intolerance of the implant lens). • Age : > 18 years • Signed informed consent • Preoperative myopia less than 10 diopters • Implantation of the CT Lucia IOL at least six months earlier 
Exclusion criteria
 
 • History of uveitis • Ocular pathology or history that could influence the biometry of the effective lens position, such as ocular trauma with zonulolysis, congenital iris- or lens defects etc. • Any eye condition influencing the lens position (to be specified) according to the investigator
Device Name	CT LUCIA hydrophobic C-loop IOL: CT Lucia® 601P (hydrophobic acrylic with heparin coated surface)

Principle Intended Use	All devices are CE marked and used within their claimed intended use. In general, all devices are intended to be used during ophthalmic surgery.
Manufacturer Name	CT LUCIA 601P

5. INTRODUCTION

Preface

In Belgium, approximately 120 000 cataract surgeries are performed annually. During this surgery, the lens is removed from its bag, and replaced by an intra-ocular lens (IOL). Older types of IOLs are made from non-foldable PMMA, requiring to make a large incision the eye. Modern types of IOLs are made from foldable acrylic material, allowing the insertion of the IOL through an incision as small as 1.8 mm. Preferably, the IOL is inserted in the lens bag, but in approximately 1 in 500 surgeries, a break of the posterior lens capsule occurs. When this complication occurs, it may not be possible anymore to use an in-the-bag implantation. In this case, the IOL can be inserted in front of the anterior lens bag (and behind the iris), which is named "in-the-sulcus" implantation. If no lens capsule is available, as a last resort the IOL can be clipped on the anterior side of the iris, using a dedicated "irisclaw" IOL. Such complicated surgeries are usually referred to the vitreoretinal department in third-line care centers. In our center, we treat such referred complicated cases weekly.

Another condition where implantation of an IOL in the sulcus may be required is when the implanted IOL (in the bag) opacifies or is not tolerated by the patient (mostly in case of multifocal IOL). In such case, the IOL is usually removed from the bag and replaced by an IOL in the sulcus.

Requirements of sulcus IOLs

For optimal performance and stability, the following properties are preferred for an IOL that is inserted in the sulcus:

- A relatively large optical part of ≥ 6 mm to avoid entrapment of the pupil behind the optic of the IOL
- An angulated IOL design that brings the optic of the IOL backward in order to avoid contact with the posterior side of the iris and also to avoid entrapment of the pupil
- A large IOL total diameter, since the diameter of the sulcus is larger than the lens bag
- A design of the IOL haptics that created a large contact area between the IOL and the sulcus
- A preloaded IOL system to avoid contamination of the IOL before and during insertion that could lead to postoperative infection (endophthalmitis). The use of a preloaded system is nowadays considered as the most effective preventive measure to avoid such serious complication.

Availability of sulcus IOLs

A few older PMMA IOL types are available that are on-label certified for use in the sulcus. However, since the use of these IOLs requires a large incision in the eye and are not preloaded, the use of these lenses is not up to the standard-of-care in modern lens surgery.

In our center, we have been using the IOL "PolyAI" from Physiol, that was certified for use in the sulcus. However, when production of this IOL was discontinued a few years ago, we had to look for a suitable alternative. At that time, a review of the commercially available

IOLs was performed, and it was decided that the IOL "CT Lucia 601" from Zeiss had all the properties that we considered as important for in-the-sulcus implantation, in spite of the lack of an official "in the sulcus" label. Also since we could not find any foldable and preloaded IOL that was officially labeled as "sulcus-IOL", we have implanted this IOL in the sulcus in ~150 patients with complicated cataract surgery. During the surgery, we found that this IOL had even better handling properties compared to the PolyAI that facilitate the in-the-sulcus positioning. It unfolds very slowly after insertion in the eye, allowing the surgeon to accurately place the IOL haptics in the desired position. Also during the postoperative visits, we assessed a very good centration and positioning of this CT Lucia 601 IOL.

Unfortunately, the IOL manufacturer (Carl Zeiss) decided last year to change the design of the CT Lucia 601, referred to as CT Lucia 611. Although this new design allows easier implantation in the bag, it makes the IOL in our evaluation less suitable for in-the-sulcus implantation. This concern was reported to and discussed with Zeiss. We have suggested to perform a post-implantation analysis study to objectively evaluate the use of the CT Lucia 601 IOL as a sulcus lens. Zeiss has agreed to continue the delivery of the CT Lucia 601 for this purpose.

Study expenses

Besides the examinations collected during the long-term postoperative visit, no additional study examinations are required outside of the normal standard-of-care.

The CT Lucia 601 IOL is registered by the FAGG and reimbursed by the RIZIV/INAMI in the same way as any other IOL, and is already registered in our hospital (CMM), hence there are no additional expenses involved for the patients or for the RIZIV/INAMI that have this IOL implanted. Also, inclusion in the study will be done post-interventionally, hence the vitrectomy surgery itself is not part of the study.

6. OBJECTIVES

The purpose of the study is to collect data that are parameters of post-IOL implantation safety:

- Questionnaire on subjective quality of vision
- Centration and anteroposterior position of the IOL (using biometry)
- Presence and quantification of any inflammation or pigment present in the anterior chamber (flare meter)
- Refractive outcome, with calculation of customized A-constant of the CT Lucia 601 IOL in-the-sulcus and quantification of higher-order aberrations (HOA)
- General safety-parameters:
 - Visual acuity
 - Intra-ocular pressure
 - Presence of macular edema or retinal nerve fiber layer (RNFL) thinning (SD-OCT)
 - Any adverse ophthalmic events

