8.2. Inclusion criteria

- Patients who had implantation of a CT Lucia 601 lens for different reasons:
 - During vitrectomy to treat a complicated cataract surgery and had the implantation of a CT Lucia 601 IOL in the sulcus or patients
 - During phaco surgery with a posterior capsule tear that necessitated the implantation of the implant lens in the sulcus
 - Explantation of an in-the-bag lens and implantation of a CT Lucia 601 as replacement lens (e.g. to treat opacification of the implant lens or intolerance of the implant lens).
- Age : > 18 years
- Signed informed consent
- Preoperative myopia less than 10 diopters
- Implantation of the CT Lucia IOL at least six months earlier

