11 CLINICAL INVESTIGATION ASSESSMENTS

11.1. Investigation Characteristics

❖ The following post-operative parameters will be collected:

- Indication of the surgery with implantation of the lens in the sulcus
- Refraction: objective and subjective
- Best Corrected Visual Acuity (BCVA)
- Pneumotonometry: intra-ocular pressure
- Biometry (using Zeiss IOLmaster 700 SS-OCT) to assess the position of the IOL in relation to the cornea (anterior chamber depth).
- Oculus Pentacam to determine IOL positioning relative to the iris
- SD-OCT: to assess the potential presence of macular edema and RNFL thinning
- Anterior chamber flare meter (Kowa) to determine the presence and quantification of any inflammation or pigment dispersion present in the anterior chamber
- Aberrometry to quantify HOA caused by IOL tilting/decentration

Note that all of the above investigation are non-contact measurements, hence without any risk of adverse events.

❖ Questionnaire about subjective quality of vision at least 6 months postop

- The patient will be asked to grade the quality of vision, at the time of completion, with a score of one to five according to the score system below:

- The questionnaire will be completed during the study visit

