13.5. Procedure for accounting for missing, unused and spurious data

Missing data will be reported with reasons given where available, and the missing data pattern will be examined. We will explore the mechanism of missing data by means of logistic regression models which will explore if missingness (i.e. whether the primary outcome is missing or not) is related to measured baseline variables. Covariates found to be predictive of missingness will, where appropriate, be included as a covariate in the analysis model.

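### Section 11.1 names no pre-implantation value and no implanted lens power: safety findings can be compared only with the fellow eye, and the A-constant objective lacks a named input

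*Combined protocol and SAP*

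**What the plan says.** Section 6 lists the parameters meant to describe safety after implantation. One is the refractive outcome, including "calculation of customized A-constant of the CT Lucia 601 IOL in-the-sulcus". Another, under the general safety items, is "Presence of macular edema or retinal nerve fiber layer (RNFL) thinning (SD-OCT"), alongside visual acuity and intra-ocular pressure.

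Section 11.1 itemises the data and introduces them with "The following post-operative parameters will be collected". The list holds the surgical indication, "Refraction: objective and subjective", BCVA, pressure, biometry, Pentacam, SD-OCT, flare and aberrometry, followed by a questionnaire. The biometry entry reads "Biometry (using Zeiss IOLmaster 700 SS-OCT) to assess the position of the IOL in relation to the cornea (anterior chamber depth").

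Sections 4 and 7 provide for one study visit, at least 6 months after the operation. Section 9.2 makes the contralateral eye, if it has no CT Lucia 601, the control.

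Two places look back before the visit. Section 8.2 requires "Preoperative myopia less than 10 diopters", and section 13.5 asks whether missingness "is related to measured baseline variables".

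**The concern.** The primary endpoint in section 4 is whether the lens can be used safely in the sulcus. Acuity, pressure, macular state and RNFL bear on that only if a finding at the visit can be placed before or after implantation. One late measurement per eye, with no earlier value, does not allow this.

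Many study eyes come from complicated cataract surgery followed by a vitrectomy that section 7 describes as usually urgent. Section 8.3 does not exclude optic nerve or macular disease as such. A thin RNFL or a poor acuity at the visit may therefore be older than the lens. Counting it against the lens would overstate harm. Dismissing it as old would understate harm. The listed data cannot settle which applies.

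The A-constant objective has a separate and simpler gap: one of its necessary inputs is not named for collection.

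**Working it through.** The plan states no figure on this point that could be reproduced. Section 13.2 justifies 100 patients by the exploratory aim and gives no effect size, SD or power. The check therefore sets the objectives against the data items.

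**A-constant.** As general method (an assumption, not stated in the documents), a lens constant is back-calculated from implanted power, axial length, keratometry and achieved refraction.

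- Achieved refraction: listed in 11.1.
- Biometry: listed, but its stated purpose is lens position. Axial length and keratometry are not named as outputs.
- Implanted power: not named in 11.1 or anywhere else in the supplied text.
- Formula for the constant: not given.

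**Safety outcomes.** Write the study-minus-fellow-eye difference at the visit as D = P + C + L, where

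- P is the difference between the eyes already present before the complication or implantation,
- C is the effect of the complication and of the surgery itself,
- L is what happened afterwards with the lens in place.

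The plan observes D only. A larger sample reduces the standard error of D but leaves P + C inside it.

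With a pre-implantation value Y0 and a visit value Y1 in the same eye, Y1 − Y0 removes P. It also removes any part of C that had already occurred when Y0 was measured. The effect of the implanting operation remains mixed with L, so the change narrows the attribution problem without fully solving it.

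**What the fellow eye can do.** With the 5% two-sided level from section 13.3 and an assumed 80% power, the detectable mean paired difference, in SDs of the within-pair difference, is (1.960 + 0.842)/√n.

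- n = 100 pairs: 2.802/10 = 0.28 SD.
- n = 50 pairs (assumed, if only half the patients have a usable fellow eye): 2.802/7.071 = 0.40 SD.

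A moderate RNFL deficit between eyes could therefore be detected without any earlier value. These figures concern detection. They say nothing about the cause of a difference once it is found.

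**Definition.** No section defines RNFL thinning by a cut-off, by change or by between-eye difference. Section 13.1 does not describe a fellow-eye analysis of it.

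**Section 13.5.** The missingness model needs baseline variables. Section 11.1 contains the surgical indication, and section 13.1 mentions age, so the model has some inputs. No pre-implantation ocular measurement is among them.

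**The case against.** The strongest reply is that section 11.1 is not a complete data list. Age is used in section 13.1, adverse events are an objective in section 6 and go on the CRF under section 19.5, and preoperative myopia is needed for eligibility. None of these appears in 11.1, so absence from it does not prove that an item will not be collected. The eCRF, Appendix B and the flow chart that section 4 cites are not in the supplied text and could hold more. This reply stands, and it limits what can be claimed.

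A reader might infer that the A-constant cannot be calculated at all. The documents do not support that. The study is single-centre and described as retrospective, the centre implanted these lenses itself, and nothing bars reading the power from the surgical record. The gap is largely one of missing detail.

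A reader might also infer that RNFL thinning cannot be shown. That goes too far as well. The plan asks whether thinning is present, and the fellow eye allows a cross-sectional comparison. What cannot be shown is change within an eye.

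The fellow eye does not answer the attribution question. It did not necessarily share the complication or the vitrectomy, it may differ from the study eye for older reasons, and it cannot serve as control if it also has the lens.

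**Conclusion.** The point holds as a cheap improvement that should be made. As itemised, BCVA, IOP, macular and RNFL findings can be compared only between eyes, and damage that preceded implantation cannot be separated from damage after it. Implanted lens power is a smaller, firm omission from the list.

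No numerical size can be given for the attribution problem, because it depends on how much disease was present beforehand and the documents do not say. The conclusion rests on three assumptions: that the unsupplied forms do not already contain these items, that an A-constant needs the inputs listed above, and that some pre-implantation values exist in the charts.

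It would be wrong to conclude that section 13.5 has no baseline variables to work with. It has at least indication and age, and lacks only earlier ocular measurements.

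**What to change.** Add the following to section 11.1, and to the eCRF that section 12.3 says will be built for the study:

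- From the chart: implanted IOL power, and the latest pre-implantation BCVA, IOP and SD-OCT where they exist, each with its date.
- From biometry: axial length and keratometry, named as outputs, with the formula to be used for the A-constant.

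In section 13.1, state that acuity, pressure and OCT outcomes will be reported as within-eye change, or adjusted for the pre-implantation value. Do not adjust for any value measured after implantation: it may already carry an early effect of the lens, and adjusting could remove that effect from a safety result. Interpret BCVA change with care, since the earlier acuity may be lowered by the condition that led to surgery.

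Where no earlier OCT exists, report the paired study-minus-fellow-eye RNFL difference, using only fellow eyes without the lens, and call it asymmetry rather than thinning due to the lens. State how many eyes fall in each set.

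The cost is a short extraction form and a plan amendment, with no extra examination for the patient. Records have to be consulted anyway for preoperative myopia. The downside is that pre-implantation OCT will be missing for some urgent cases, so the change analysis will cover a subset that may not represent all study eyes.

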7. CLINICAL INVESTIGATION DESIGN

Inclusion of the patients will be done post-interventionally: patients that underwent a (usually urgent) vitrectomy to treat a complicated cataract surgery with the implantation of a CT Lucia 601 IOL in the sulcus will be asked to participate in this clinical trial.

For this trial, one additional long-term postoperative visit (at least 6 months after the vitrectomy) will be required besides the standard-of-care visits. During this study visit, besides the standard ophthalmological clinical examination and a questionnaire about subjective vision quality, the following technical examinations will be performed:

1. Biometry (using Zeiss IOLmaster 700 SS-OCT and Oculus Pentacam) to assess the position of the IOL in relation to the cornea (centration and anterior chamber depth).
2. SD-OCT to assess the potential presence of macular edema or retinal nerve fiber layer (RNFL) thinning.
3. Anterior chamber flare to determine the amount of inflammation and pigment dispersion present in the anterior chamber (using Kowa Flare Meter).
4. Quantification of HOA using iDesign Hartmann shack aberrometer

8. CLINICAL INVESTIGATION POPULATION

8.1. Number of participants

A total of 100 patients will be included.

Estimated enrolment time is 12 months

8.2. Inclusion criteria

- Patients who had implantation of a CT Lucia 601 lens for different reasons:
 - During vitrectomy to treat a complicated cataract surgery and had the implantation of a CT Lucia 601 IOL in the sulcus or patients
 - During phaco surgery with a posterior capsule tear that necessitated the implantation of the implant lens in the sulcus
 - Explantation of an in-the-bag lens and implantation of a CT Lucia 601 as replacement lens (e.g. to treat opacification of the implant lens or intolerance of the implant lens).
- Age : > 18 years
- Signed informed consent
- Preoperative myopia less than 10 diopters
- Implantation of the CT Lucia IOL at least six months earlier

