8.3. Exclusion criteria

- History of uveitis
- Ocular pathology or history that could influence the biometry of the effective lens position, such as ocular trauma with zonulolysis, congenital iris- or lens defects etc.
- Any eye condition influencing the lens position (to be specified) according to the investigator

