9.3. Randomisation

All patients who received a CT Lucia 601 at least 6 months ago will be contacted and asked for participation in our clinical trial. There will be no randomization necessary since we only plan one postoperative non-invasive visit without performing an invasive intervention or using a study drug. All patients will undergo the same technical examinations.

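### The plan has no rule for eyes re-operated after the CT Lucia 601 was implanted, so failures of sulcus placement can drop out of the safety conclusion

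*Combined protocol and SAP*

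**What the plan says.** The primary endpoint in section 4 is to "determine whether the CT Lucia 601 IOL can be used safely in the sulcus". Section 6 lists the data that bear on this: lens centration and position, flare, refraction with a customised A-constant, higher-order aberrations, visual acuity, pressure, OCT findings and adverse ophthalmic events. All examinations take place at one visit.

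Eligibility in section 8.2 is timed from the implantation: "Implantation of the CT Lucia IOL at least six months earlier". Section 9.3 uses the same anchor for recruitment: "All patients who received a CT Lucia 601 at least 6 months ago will be contacted". The visit is timed from a different event. Section 4 has "A single late-postoperative visit, scheduled ≥ 6 months after the vitrectomy", and section 7 says that "one additional long-term postoperative visit (at least 6 months after the vitrectomy) will be required".

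Section 8.3 has two exclusions on lens position: "Ocular pathology or history that could influence the biometry of the effective lens position", with trauma and congenital defects as examples, and "Any eye condition influencing the lens position (to be specified) according to the investigator". Neither names re-operation.

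The only surgical item among the parameters in section 11.1 is the reason for the index operation. Section 13.7, on inclusion in analysis, says only who will be contacted. Section 19.5 covers safety issues that arise during the investigation. Section 9.2 takes the fellow eye without the lens as control and sets no minimum time since any surgery on it.

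**The concern.** A sulcus lens that has had to be repositioned, exchanged or taken out is among the most informative outcomes for a study of whether sulcus placement is safe. Patients enter at least six months after implantation, so some of these events may already have happened by the visit. A cross-sectional examination sees only the present state of the eye. A lens that slipped and was surgically re-centred can look well centred, and a lens that was replaced is no longer there to examine. Unless the history is collected and a counting rule is stated, these eyes contribute a good measurement, a measurement of another lens, or nothing.

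A second effect concerns inflammation. Flare and macular edema respond to recent surgery. An eye implanted two years ago and operated on again last month meets the six-month rule, yet its flare value may reflect the recent procedure. In the study eye this inflates the apparent harm. In the control eye it hides a true difference.

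**Working it through.** **1. Is there a rule?** The plan offers no figure to reproduce, because it gives no re-operation rate and no sample-size calculation. The check is therefore first one of reading.

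- Time anchor: section 8.2 counts from implantation, and sections 4 and 7 count from the vitrectomy. For the vitrectomy route these are the same operation. The phaco route with a capsule tear and the lens-exchange route need not include a vitrectomy, so for those patients the anchor in sections 4 and 7 can be undefined.
- Clock: no section restarts the six months after a later operation.
- Lens status: no section requires the CT Lucia 601 to be in the sulcus at the visit. Explantation is mentioned only for the earlier in-the-bag lens.
- Data: section 11.1 has no item for later surgery. Section 6 lists adverse ophthalmic events without a look-back period. Section 19.5 covers only the investigation, which for each patient is one visit.
- Outcome: no section counts re-operation as a safety result.

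**2. What can happen to a re-operated eye?** (a) It is enrolled and pooled, with no field that marks the failure. (b) The investigator excludes it under section 8.3. Under (a) the failure stays in the denominator but is not in the numerator. Under (b) it is in neither.

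**3. Size, for illustration.** Assumption: a re-operation rate r of 1% to 10%, among 100 study eyes (section 8.1 gives 100 patients). Expected number: 100r. Chance of at least one: 1 − (1 − r)^100. Intervals are exact (Clopper-Pearson) 95%. With no events the upper limit is 1 − 0.025^(1/n): for n = 100 this is 3.6%, for n = 95 it is 3.8%.

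| Assumed r | Chance of ≥ 1 in 100 | Counted (95% CI) | Enrolled, not recorded (upper limit) | Dropped, not replaced (upper limit) |
|---|---|---|---|---|
| 1% | 63% | 1/100 (0.0–5.4%) | 0/100 (3.6%) | 0/99 (3.7%) |
| 3% | 95% | 3/100 (0.6–8.5%) | 0/100 (3.6%) | 0/97 (3.7%) |
| 5% | 99% | 5/100 (1.6–11.3%) | 0/100 (3.6%) | 0/95 (3.8%) |
| 10% | >99.9% | 10/100 (4.9–17.6%) | 0/100 (3.6%) | 0/90 (4.0%) |

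In the cohort of about 150 patients in section 5, the same rates give 1.5, 4.5, 7.5 and 15 expected cases. That figure refers to complicated cataract surgery and may not include the exchange route.

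**4. Effect on the averages.** Suppose a fraction f of eyes differs in lens position by D standard deviations (assumed 1 to 3). The pooled mean moves by f × D, and the SD is multiplied by √(1 + f(1 − f)D²). At f = 0.05 the shift is 0.05 to 0.15 SD and the SD rises by 2.3% to 19.5%. Over f = 0.01 to 0.10 the shift is 0.01 to 0.30 SD and the SD rises by 0.5% to 34.5%. At low rates the averages move little. The loss is in the count of failures.

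**The case against.** The strongest reply is that section 8.3 already deals with these eyes. It looks at ocular history and at current eye condition, and an investigator could readily apply it to a repositioned or replaced lens. This stands against one tempting inference, that eligibility looks only at the index operation and admits anyone implanted long enough ago. The documents do not say that. But section 8.3 does not name re-operation and leaves its second criterion to be specified, so the result is discretionary. Where it is applied, it removes failures of the very outcome under study.

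A reader might also infer that re-operated eyes will be measured as though the first placement had held. That is one possible outcome, not what the plan prescribes. The visit includes a standard clinical examination and imaging of the lens relative to the iris, so an iris-claw replacement is unlikely to pass unnoticed. A surgically re-centred lens is not so easily recognised without the surgical record.

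Third, adverse ophthalmic events are a listed safety parameter and could capture a re-operation. Some cases may be caught this way. Nothing secures it, since there is no look-back period and no matching field.

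Finally, not every removal is a position failure. The protocol itself gives opacification and intolerance as reasons for removing a lens. This stands, and it means that the reason for re-operation has to be recorded.

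**Conclusion.** The gap is real and should be closed before data lock. The plan does not say whether eyes re-operated since implantation are included, excluded or counted as failures, and both courses open to the investigator can lose failures from the safety conclusion. The mismatch between section 8.2 and sections 4 and 7 is on the page and needs no assumption. The possible distortion of the flare and OCT comparison follows from the absence of any minimum time since last surgery in either eye.

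The size is not known. The contrast of 5/100 with 0/100 or 0/95 rests on an assumed 5% rate, on a failure endpoint that the plan does not define, and on no other failure being seen. It shows scale and does not predict a result. The documents do not support the stronger statement that the trial will report displaced lenses as successes. They support only that nothing in the plan prevents these failures from going uncounted.

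**What to change.** - **Section 11.1:** add, per eye from the surgical record, whether the CT Lucia 601 is in situ; any repositioning, exchange or removal, with date and reason; and the date of the last intraocular surgery.
- **Section 8.3:** state that the lens-position exclusions apply to conditions present before implantation, not to displacement or re-operation after it. Without this, the eyes never reach the denominator.
- **Safety outcome:** report re-operation by reason over all enrolled eyes and, where records and approvals allow, over all implanted eyes, so that patients who decline the visit are not lost from the count. Count as position failures only re-operations done for position.
- **Sections 13.1 and 13.7:** summarise biometry, A-constant and aberrations in eyes with the implanted lens undisturbed, with a sensitivity analysis that includes repositioned eyes.
- **Sections 4 and 7:** reconcile the visit anchor with section 8.2. Time since implantation is defined for all three entry routes.
- **Flare and OCT:** restrict the comparison, or a sensitivity analysis of it, to study and control eyes at least 6 months from their last intraocular surgery.

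The cost is protocol wording and a few eCRF fields filled from existing records, with no added examination. A few eyes may be missing from the flare and OCT comparison, and the safety result may be less favourable. Section 13.6 leaves the statistical plan open until data lock, so the counting rules can still be set there. The changes to eligibility and collected data need an amendment.
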